12.2.12 Procedures on End of study visit (Day 14)

- Subjects will come to the Clinical site for an ambulatory End of study visit
- Subjects will undergo a complete physical examination including documenting weight
- Subjects will provide nasopharyngeal and oropharyngeal swab which will be tested for the presence of SARS-COV-2 infection with a rapid antigen test
- Subjects will have their vital signs (heart rate, blood pressure, respiratory rate, body temperature) recorded
- Subjects body weight will be measured
- Subjects will provide blood and urine samples for laboratory analysis (biochemistry, hematology, coagulation, urinalysis); the urine sample will be used also for drug screen test and cotinine test performed via dip stick
- Subjects will undergo a 12-lead ECG
- Subjects will undergo a breath alcohol test
- Blood samples will be collected for PK analysis according to the sample schedule in section 12.4.1 Blood samples collection
- Adverse events (AEs) that have occurred will be recorded
- Concomitant medication intake will be recorded
- Subjects will complete the study and their participation will be ended

Every effort must be taken to ensure that subjects terminating the study prematurely undergo the safety checks of the follow-up visit. If subjects terminating the study prematurely due to an AE, every effort must be taken to monitor the subjects until the AE has resolved.

12.3 Safety and tolerability assessments

Only healthy subjects are eligible for the study. The healthy status will be determined by meeting the inclusion and exclusion criteria. Subjects' safety will be monitored during the study. Adverse events will be monitored and recorded throughout the study.

Prior to the first benfo-oxythiamine (B-OT) dosing only, the Principal Investigator or a delegated medical doctor will assess the clinical significance of results of laboratory investigations for hematology and serum chemistry values outside the defined normal ranges, as provided by the laboratory.

In addition to the planned times, any safety procedures can be performed at any time considered necessary by the Principal Investigator or a delegated medical doctor.

At least one qualified physician will be present at all times during each confinement day of each cohort. In addition, an ambulance and an emergency doctor will be available on each dosing day for a period of 12 hours (from 08:00 am until 08:00 pm) for the SAD part and for a period of 4 hours for the MAD part at the site and on call during the rest of the study. Also, two cardiologists will remain available on call at all times during the entire period of the study. In case any clinically significant abnormality is observed at pre-dose, Principal Investigator or

a delegated medical doctor will decide whether the subject will proceed to investigational product administration or will be withdrawn from the study.

Safety will be assessed by consideration of all adverse events reported by or elicited from the subject and abnormalities detected on physical examinations, safety blood tests, urinalysis, vital signs and 12-lead ECG.

All adverse events (serious and non-serious) beginning prior to dosing through follow-up visit will be recorded in the subject's source documentation and CRF.

The definitions, reporting and follow-up of AEs, SAEs and potential pregnancies are described in section 13.1.

12.3.1 Vital Signs

Evaluations of systolic and diastolic blood pressure, pulse rate, respiratory rate, and body temperature will be performed throughout the study. Pulse and blood pressure will be taken after 5 minutes in the supine position.

12.3.2 Weight and height

Weight (kg), height (cm) and body mass index (BMI) will be recorded/calculated at screening.

12.3.3 Physical examination

Physical examination (including general appearance, head, ears/eyes/nose/throat/neck, skin, respiratory system, cardiovascular system, gastrointestinal (including mouth) system, musculoskeletal system, central and peripheral nervous systems, and lymph nodes) will be performed by the Investigator(s) or a designee. Other body systems can be examined if required, at their discretion of the Investigator. Clinically relevant findings that are present prior to the first study drug administration must be recorded with the subject's Medical History. Clinically relevant findings found after study drug administration and meeting the definition of an AE (new AE or worsening of previously existing condition) must be recorded.

12.3.4 Electrocardiography

A complete standard 12-lead ECG will be recorded by a member of the investigator's team under the following conditions:

- Supine position of the subject for at least 5 minutes rest
- Use of a computerized ECG device
- Automatic calculation of the following parameters: heart rate, PR interval, QRS width, QT interval, and QTcF (calculated using Fredericia's formula)
- ECG printouts will be examined and interpreted by the investigator on the day of recording. This analysis performed by the investigator has to be entered in the eCRF. Any new clinically relevant abnormality that occurred after signing the informed consent will be documented as an AE.

The investigator will assess the ECG recording as 'normal', 'abnormal – not clinically significant', or 'abnormal – clinically significant' and include a description of the abnormality as required. ECG printouts will be collected and stored at the site. Each ECG trace should be labelled with the study number, subject number, subject initials and date of birth.

12.3.5 Laboratory assessments, drug screen and breath alcohol test

Routine laboratory safety samples will be analyzed by the local laboratory Bodimed Ltd. The site will be supplied with kits for sample collection, requisition forms for sample shipment to analytical site and a laboratory manual with instructions for collection and handling of the

samples. The analysis of urine will be done at the site with urine dip stick tests, which will be purchased by the site team prior to the initiation of the study.

Printed laboratory reports will include normal reference ranges. A decision regarding whether the result outside the reference range is of clinical significance or not shall be made by an Investigator and the report will be annotated accordingly. Clinically significant abnormalities at screening or occurring during the study will be recorded on the AE page. The reference ranges for laboratory parameters will also be filed in the Investigator site file.

The laboratory results should be signed and dated and retained at clinical research site as source data for laboratory variables.

Any clinically significant deviation of laboratory parameters from reference ranges will be documented in the source documentation and in the eCRF and followed up, by the Principal Investigator or authorized investigator. Re-test of the safety laboratory parameters may be done under Investigator's discretion.

Blood and urine samples will be collected for the following safety clinical laboratory tests as listed in Table 3:

TABLE 3: SAFETY PARAMETERS

Laboratory Test/Safety Procedure	Parameters
SAD Part	
Hematology	Haemoglobin (HGB), Mean corpuscular volume (MCV), Mean corpuscular haemoglobin (MCH), Mean corpuscular haemoglobin concentration (MCHC), hematocrit (HCT), red cell count (RBC), white blood cells (WBC) neutrophils (NEUT), lymphocytes (LYMP), monocytes (MONO), eosinophils (EOS), basophils (BASO) and platelets (PLT).
Chemistry and electrolytes	Sodium, potassium, calcium, inorganic phosphate, total protein, albumin, glucose ¹ , triglycerides, blood urea nitrogen (BUN), creatinine, uric acid, total bilirubin ² , alkaline phosphatase, AST, ALT gamma-GT and LDH.
Serology	HIV1 and HIV2 antibodies, Hepatitis B surface antigen, Hepatitis B antibodies and Hepatitis C antibodies
SARS-COV-2 (COVID – 19) infection	Polymerase Chain Reaction method for detection of the virus
Urinalysis (will be done using dip stick test at the site)	Leucocytes, blood, nitrite, protein, urobilinogen, bilirubin, pH, specific gravity, ketones, glucose.
Alcohol	Alcohol Breath Test
Urine drug screen	Cocaine, amphetamines, opiates, benzodiazepines and cannabinoids.
MAD Part	
Hematology	Haemoglobin (HGB), Mean corpuscular volume (MCV), Mean corpuscular haemoglobin (MCH), Mean corpuscular haemoglobin concentration (MCHC), hematocrit (HCT), red cell count (RBC), white blood cells (WBC) neutrophils

	(NEUT), lymphocytes (LYMP), monocytes (MONO), eosinophils (EOS), basophils (BASO) and platelets (PLT).
Coagulation	Fibrinogen, prothrombin time (PT), activated partial thromboplastin time (aPTT)
Chemistry and electrolytes	Sodium, potassium, calcium, inorganic phosphate, total protein, albumin, glucose ¹ , triglycerides, blood urea nitrogen (BUN), creatinine, uric acid, total bilirubin ² , alkaline phosphatase, AST, ALT gamma-GT and LDH.
Serology	HIV1 and HIV2 antibodies, Hepatitis B surface antigen, Hepatitis B antibodies and Hepatitis C antibodies
SARS-COV-2 (COVID – 19) infection	Rapid antigen test for detection of the virus
Urinalysis (will be done using dip stick test at the site)	Leucocytes, blood, nitrite, protein, urobilinogen, bilirubin, pH, specific gravity, ketones, glucose.
Alcohol	Alcohol Breath Test
Urine drug screen	Cocaine, amphetamines, opiates, benzodiazepines and cannabinoids, barbiturates.

Urine drug test will be performed on site with a dip stick test and will include amphetamine, barbiturates, benzodiazepines, cocaine, cannabinoids, opioids and nicotine. At time-points when both urinalysis and drugs of abuse screening is required, all testing will be performed from a single sample.

An alcohol breath test will be conducted on site using a breathalyzer. The results of the test will be recorded in each subject's source documents and eCRF. Only subjects with a "0%" result will be considered to have a negative test result.

A full chain of custody will be maintained for all samples throughout their lifecycle.

The investigator will ensure full traceability of collected biological samples from the subjects while in storage at the center until shipment and will keep documentation of receipt of arrival.

The sample receiver will keep full traceability of samples while in storage and during use, until used, disposed of, or until further shipment or disposal (where appropriate) and will keep documentation of receipt of arrival.

12.3.6 Concomitant medications

In this study, limited types of concomitant medications are permitted. Adjustment of routine medications taken by subjects should be avoided during study participation except when subject safety could be affected by lack of adjustment

Concomitant medications initiated or stopped for an AE will be recorded in the source documentation and CRF of the relevant subject.

If a concomitant medication is used after the first treatment administration an investigator or delegate and/or the sponsor will decide whether the subject will be permitted to remain in the study, depending on the drug used, the time of drug intake, etc.

12.4 Pharmacokinetic and pharmacodynamics assessments

12.4.1 Blood samples collection

Blood samples for PK and PD determination will be processed, stored, and shipped according to the sample processing instructions supplied by the bioanalytical facility. All blood samples will be drawn using an indwelling IV catheter or by venipuncture. After blood sample collection from the IV catheter, the catheter will be flushed with a 0.9 % w/v NaCl solution to avoid obstruction (without Hep Lock). The indwelling IV catheter will not be left in situ for more than 24 hours, except during treatment period. If the intravenous catheter is not available for use and/or has been in place for > 24 hours, samples will be drawn by venipuncture, except during the treatment period.

SAD Study part:

PK blood samples (5 mL) for determination of plasma benfo-oxythiamine (B-OT), oxythiamine (OT) or other derived metabolites concentrations will be taken into pre-labelled EDTA collection tubes at the time points indicated in the Visit and Assessment Schedule (Table 1).

The quantitative determination of B-OT and OT in human plasma will be performed by using a validated method.

Samples should be maintained at 4 °C (\pm 4 °C) during the whole procedure from sample collection until sample freezing.

Samples will be cooled in an ice/water bath or cooling device until processed, centrifuged at approximately 1900 g (\pm 38g) at 4°C (\pm 4°C) for 10 minutes and then placed into an ice/water bath or cooling device. The time between blood collection and placement in the centrifuge will not exceed 60 minutes.

Plasma will be divided and transferred into pre-labeled duplicate 2 mL polypropylene tubes for each analyte (B-OT and OT). The resulting 4 aliquots will be maintained in the ice/water bath or cooling device. A minimum of 0.5 mL of plasma is required for each aliquot.

Samples will be kept in an ice/water bath until transferred to the storage unit (freezer).

Then, samples will be stored and frozen at approximately -80°C (\pm 15°C) until shipment to the bioanalytical laboratory. The time between the centrifuge and placement in freezer will not exceed 60 minutes.

MAD Study part:

PK blood samples (2.0 mL) for determination of plasma oxythiamine (OT) and any other derived metabolites concentrations will be taken into pre-labelled EDTA collection tubes at the time points indicated in the Visit and Assessment Schedule (Table 2).

The quantitative determination of OT and any other derived metabolites in human plasma will be performed by using a validated method.

Samples should be maintained at 4 °C (\pm 4 °C) during the whole procedure from sample collection until sample freezing.

Samples will be cooled in an ice/water bath or cooling device until processed, centrifuged at approximately 1900 g (\pm 38g) at 4°C (\pm 4°C) for 10 minutes and then placed into an ice/water bath or cooling device. The time between blood collection and placement in the centrifuge will not exceed 60 minutes.

Plasma will be divided and transferred into pre-labeled duplicate 2 mL polypropylene tubes. The resulting 2 aliquots will be maintained in the ice/water bath or cooling device. A minimum of 0.5 mL of plasma is required for each aliquot.

Samples will be kept in an ice/water bath until transferred to the storage unit (freezer).

Then, samples will be stored and frozen at approximately -80°C (±15°C) until shipment to the bioanalytical laboratory. The time between the centrifuge and placement in freezer will not exceed 60 minutes.

In the SAD part, PD blood samples (2 mL) for transketolase activity analysis will be managed according to the instructions leaflet dated 08 Nov 2021, provided by the responsible laboratory Medical Laboratory Bremen and are the following:

- a. Collect samples in pre-labelled EDTA (2 mL) collection tubes at the time points indicated in the Visit and Assessment Schedule (Table 1).
- b. Transfer the sample material into a reagent tube of approx. 13 ml capacity, preferably made of polypropylene, e.g. SARSTED, 95 mm x 16.8 mm, article no. 55.518. Polystyrene tubes are very fragile when frozen (see below).
- c. Fill up the tube with isotonic (0.9%) NaCl solution.
- d. Centrifugation is then performed at room temperature in a standard laboratory centrifuge at approx. 2800 g, which corresponds to 3800 rpm when e.g. SIGMA 3-16P K centrifuge is used, centrifugation time is 10 min, brake acceptable.
- e. Remove the supernatant (including the buffy coat) and fill up again with isotonic NaCl solution.
- f. Then centrifuge again, when removing the supernatant, immerse about 1 mm deep into the erythrocyte sediment, fill up with isotonic NaCl.
- g. Repeat the above steps again, remove the supernatant for the last time. Mix 0.5 ml of the washed and packed erythrocytes with 0.5 ml of distilled water (not isotonic NaCl!).
- h. Mix thoroughly (e.g. VORTEX mixer 10 sec), by this step most of the erythrocytes are hemolyzed and their components are released.
- i. Freeze at -70°C until shipment to the laboratory within the planned schedule of shipments

In the MAD part, PD blood samples (5 ml) will be collected in prelabelled EDTA collection tubes at time points indicated in the visit and assessment schedule (Table 2). The samples will be prepared and analyzed according to a validated method if available.

The following blood samples (Table 4) need to be drawn for PK and PD analysis on each of the sampling days, as indicated in the Visit and Assessment Schedule (Table 1 and 2).

TABLE 4: PK/PD SAMPLING TIMEPOINTS

SAD part			
PK sample timepoint (hr.)	Allowed time deviation	PD sample timepoint (hr.)	Allowed time deviation
Pre-dose (35 min before dosing)	+/- 5 min	Pre-dose (35 min before dosing)	+/- 5 min
0.25	+/- 5 min	-	-
0.5	+/- 5 min	-	-
0.75	+/- 5 min	-	-
1.0	+/- 5 min	1.0	+/- 5 min
1.5	+/- 5 min	-	-
2	+/- 5 min	2.0	+/- 5 min
4	+/- 10 min	4.0	+/- 10 min
8	+/-15 min	8.0	+/-15 min
12	+/- 30 min	12	+/- 30 min
24	+/- 1 hr	24	+/- 1hr
36	+/- 1 hr	-	-
48	+/- 1hr	48	+/- 1hr
72	+/- 1hr	72	+/- 1hr
168	+/- 2 hr	168	+/- 2 hr

MAD part				
Day	PK sample timepoint (hr.)	Allowed time deviation	PD sample timepoint (hr.)	Allowed time deviation
1	Pre-dose (35 min before dosing)	+/- 5 min	Pre-dose (35 min before dosing)	+/- 5 min
	0.25	+/- 5 min	-	-
	0.5	+/- 5 min	-	-
	0.75	+/- 5 min	-	-
	1.0	+/- 5 min	1.0	+/- 5 min
	1.5	+/- 5 min	-	-
	2	+/- 5 min	2.0	+/- 5 min
	4	+/- 10 min	4.0	+/- 10 min
	8	+/-15 min	8.0	+/-15 min
	12	+/- 30 min	12	+/- 30 min
2	Pre-dose (35 min before dosing; 24 hr after last dosing)	+/- 30 min	Pre-dose (35 min before dosing; 24 hr after last dosing)	+/- 30min
3	Pre-dose (35 min before dosing; 24 hr after last dosing)	+/- 30 min	-	
4	Pre-dose (35 min before dosing; 24 hr after last dosing)	+/- 30 min	Pre-dose (35 min before dosing) - - - 1.0 - 2.0 4.0 8.0 12	+/- 30 min
5	Pre-dose (35 min before dosing; 24 hr after last dosing)	+/- 30 min	Pre-dose (35 min before dosing; 24 hr after last dosing)	
6	Pre-dose (35 min before dosing; 24 hr after last dosing)	+/- 30 min	-	+/- 30 min
7	Pre-dose (35 min before dosing)	+/- 5 min	Pre-dose (35 min before dosing)	+/- 5 min
	0.25	+/- 5 min	-	-
	0.5	+/- 5 min	-	-
	0.75	+/- 5 min	-	-
	1.0	+/- 5 min	1.0	+/- 5 min
	1.5	+/- 5 min	-	-
	2	+/- 5 min	2.0	+/- 5 min

MAD part				
Day	PK sample timepoint (hr.)	Allowed time deviation	PD sample timepoint (hr.)	Allowed time deviation
	4	+/- 10 min	4.0	+/- 10 min
	8	+/-15 min	8.0	+/-15 min
	12	+/- 30 min	12	+/- 30 min
8	24 hr after last dosing	+/- 30 min	24 hr after last dosing	+/- 30 min
11	96 hr after last dosing	+/- 4hr	-	-
14	168 hr after last dosing	+/- 4hr	-	-

The clock time will be recorded and reported for all blood draws and all subjects. Actual sampling time will be used for pharmacokinetic calculations. A deviation greater than the one indicated as allowed will be reported as a protocol deviation in a master protocol deviation log and its cause will be recorded.

When the following assessments are scheduled to be performed at the same time-point, the order of priority will be as follows:

1. ECG
2. Vital signs
3. Blood sampling for safety
4. Physical examination

When a PK assessment is scheduled for the same nominal time as another scheduled assessment, the PK sample will have priority, unless other procedures are necessary for assuring subject's safety.

If an assessment or collection is scheduled by day, and not by a specific time, then no time window will apply although generally the time of day should be the same throughout the study.

12.4.2 Labelling

Pre-printed, waterproof labels will be used to identify all PK and PD tubes used during blood sample collection and for storage of separated plasma. Each label will contain the following information:

- Protocol number
- Subject Number
- Study period number (e.g. D-1)
- Blood Sample Number
- Sampling time point (e.g. 0:30m; 1:00h)
- Sample type (blood or plasma) & purpose (e.g. PK)

12.4.3 Shipping procedures

The primary PK and PD samples will be stored at the clinical facility until the shipment to the respective analytical Biochemical Laboratories. The back-up samples can be shipped to laboratory only if required, after Sponsor written approval.

The CRO will arrange shipment of the PK and PD samples. Samples must be shipped to the Analytical Biochemical Laboratories at time intervals agreed with the Sponsor. The samples

will be transferred in an appropriate container packed in an adequate amount of dry ice enough to keep the samples frozen for at least 72 hours. For all shipments, the laboratory should acknowledge in writing the receipt of plasma samples in good condition.

The samples destined for retention will be stored by the clinical facility in a freezer at -80°C and will remain there until the final report is issued and the study sponsor authorization is obtained to discard the samples. The packaging of the samples will meet the Biosafety rules and IATA recommendations related to the documentation and package.

12.4.4 Determination of plasma drug concentrations and measurement of the transketolase activity

The concentration in Plasma of B-OT, OT and potential other Thiamine metabolites derivate will be determined using a validated liquid chromatography tandem mass spectrometry method and will be conducted in accordance with Good Laboratory Practice regulations and guidelines. Methods validation must be completed prior to start of the analysis.

In the SAD part, For each cohort, in preparation of the SRC, the PK analysis is conducted after all Day 2 (T=48hr) are taken. The rest of the PK samples ((T=72 and 168hr) are analysed after all PK samples are collected at the end of the study. In each run, standard and quality control samples will be distributed throughout the batch containing study samples. Samples with concentrations above the ULOQ will be diluted and re-assayed.

In the MAD part, for each cohort, in preparation of the SRC, the PK analysis will be conducted after all Day 5 samples are taken. The rest of the PK samples are analysed after all PK samples are collected at the end of the study. In each run, standard and quality control samples will be distributed throughout the batch containing study samples. Samples with concentrations above the ULOQ will be diluted and re-assayed. As B-OT was not detected in any cohort of the SAD part, the concentration of B-OT will not be assessed in the MAD. Other metabolites (e.g oxythiamine pyrophosphate) of this prodrug might however be assessed from the back up samples if a validated method has been established before the end of the study.

Full details, including the lower (LLOQ) and upper (ULOQ) limits of quantification range, will be provided in a Bioanalytical Plan

Plasma samples of withdrawn subjects should also be analyzed for drug concentrations and pharmacokinetic parameters (providing withdrawal was not due to withdrawal of consent).

Unacceptable values due to analytical reasons will be handled in accordance with the Bioanalytical Plan.

Measurement of the transketolase activity in erythrocytes will be done following the routinely established procedure to perform the analysis in Medical Laboratory Bremen in the SAD part of the study.

In the MAD part of the study transketolase activity measurement will be done according to a validated method established by the responsible laboratory if available.

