8.5 Stopping Criteria for Dose Escalation

Dose escalation will not continue to the next dose level if (a) maximal OT plasma levels are achieved, i.e. further increase is not justified from a scientific point of view, or if (b) toxicities are observed that do not justify continuation from an ethical point of view.

The study will be halted if one or more subjects experience a serious adverse event (SAE) that is considered as related to B-OT or 2 or more subjects in the same group experience severe AEs that are considered to be related to B-OT.

Dose-escalation will stop if clinically relevant signs or symptoms of similar nature occur in 2 or more subjects in a group that, in the opinion of the PI, warrant stopping of dose-escalation.

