8.6.1 Data Reviewed by Safety Review Committee for Dose Escalation Decision

The SRC will decide on the next dose levels throughout the study, considering at each decision point the degree of uncertainty. The choice of the dose levels will take into consideration an estimate of exposure levels to be achieved and potential adverse effects. Emerging C_{max} and AUC data will always be benchmarked to exposures expected at key human predicted doses (PAD/ATD). Late emerging safety issues that may have occurred after the time point for the dose escalation decision will always be considered.

In the SAD part of the study, at every SRC meeting, cumulative data for all cohorts will be reviewed. The following data will be reviewed for each individual cohort:

- Safety and tolerability data for 4 days for at least 3 healthy volunteers in the 2 first cohorts and 5 healthy volunteers in the next cohorts.
- PK data for 48 hours for at least 3 or 5 healthy volunteers in the first or next cohorts respectively.

Appropriate data collection up to 7 days in a given dosing cohort should be complete to proceed to the next dose cohort.

In the MAD part of the study, at every SRC meeting, cumulative data for all cohorts will be reviewed. The following data will be reviewed for each individual cohort:

- Safety and tolerability data for 8 days for at least 5 healthy volunteers in each cohort.
- PK data for 96 hours for at least 5 healthy volunteers in each cohort.

Appropriate data collection up to 14 days in a given dosing cohort should be complete to proceed to the next dose cohort.

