8.6.2 Safety Review Committee Decision on Next Dose

The SRC will take the decision for the next dose level or whether to stop the study after reviewing all the pertinent safety and any other relevant data.

If consensus among the voting SRC members cannot be reached then the PI, who has the ultimate responsibility for the safety of the healthy volunteers, will make the final decision on the next dose level or whether to stop the study. In any event, dose escalation can only occur if agreed by the PI.

The decisions of the SRC on the next dose level will be documented and provided to all the appropriate parties involved with the study, including the Pharmacist to enable IMP preparation for the next scheduled dosing day.

- Where stopping criteria have not been met, the decision of the SRC may be to give the next higher dose according to the predefined dose increment, a smaller dose than previously given, a repeated dose or to stop dosing.
- A dose in which the safety stopping criteria have been met will not be repeated and further dose escalation **must not** occur.
 - In this case, the SRC will review the totality of data and restart of dosing is possible without a substantial amendment (e.g., in the case of a laboratory error) if SRC review concludes that the relevant stopping criterion was not fulfilled.
 - A lower dose level expected to be tolerable and not to meet the stopping criteria, would be acceptable in this case.
 - If the safety stopping criteria are met and the SRC decides that there are reasons that the dose level should be repeated or further dose escalation is warranted a summary of the data and justification (CSP amendment) will be submitted to the ESB, the Regulatory Authority and the IEC/IRB for their approval before further dosing.
- In some circumstances, consideration can be given to test fractionated or split doses.

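### Each MAD escalation is decided on OT PK to Day 5; assaying the already drawn Day 6–8 samples first would give the SRC measured repeated-dose exposure at modest cost

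*Protocol*

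**What the plan says.** In the MAD part, full OT profiles are taken on Day 1 and Day 7 only. Days 2 to 6 have one pre-dose sample each, and Days 8, 11 and 14 one sample each after the last dose (Protocol Tables 2 and 4).

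The PK cut-off for escalation is the same everywhere. Protocol 8.1.2 and SAP 4.1.2 tie escalation to PK at Day 5. Protocol 8.6.1 asks for "PK data for 96 hours for at least 5 healthy volunteers in each cohort"; the Day 5 pre-dose sample falls 96 h after the first dose. Protocol 12.4.4 says that "in preparation of the SRC, the PK analysis will be conducted after all Day 5 samples are taken", and then: "The rest of the PK samples are analysed after all PK samples are collected at the end of the study".

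The other requirements run later. Protocol 8.4 needs all six subjects to have finished the seven days of dosing. Protocol 8.6.1 asks for "Safety and tolerability data for 8 days for at least 5 healthy volunteers in each cohort" and adds: "Appropriate data collection up to 14 days in a given dosing cohort should be complete to proceed to the next dose cohort".

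On the use of PK, 8.6.1 says that emerging Cmax and "AUC data will always be benchmarked to exposures expected at key human predicted doses", and 8.5 says: "Dose escalation will not continue to the next dose level if (a) maximal OT plasma levels are achieved". Under 8.6.2 the SRC decides "after reviewing all the pertinent safety and any other relevant data". No reason is given for stopping the assay at Day 5.

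**The concern.** The SRC judges whether the next repeated dose is acceptable, yet its planned PK package holds Cmax and AUC after a single dose only. Exposure at the end of dosing has to be projected from the Day 1 profile and the troughs. The samples that would measure it are drawn before the decision, but nothing in the plan requires them to be assayed by then.

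Two comparisons sharpen this. In the SAD part the same kind of cut-off deferred only the 72 h and 168 h samples, so that SRC had the main profile at the dose under review. And SAP 8.2.1 judges steady state from the pre-dose samples of Days 4, 5, 6 and 7, of which the SRC's package holds only Days 4 and 5.

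At stake is the exposure check on the way up to 5 mg. Protocol 8.3 quotes a margin of 7.6 at 1 mg, from SAD PK against steady-state exposure at the dog NOAEL. That margin thins as the dose rises.

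**Working it through.** **1. Sample counts** (Protocol Tables 2 and 4). Day 1: 10. Days 2–6: 5. Day 7: 10. Days 8, 11 and 14: 3. Total 28, and 28 × 2 mL = 56 mL, which reproduces the PK line of Table 5.

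- To Day 5: 10 + 4 = 14 per subject, or 84 per six-subject cohort.
- To Day 8: 14 + 12 = 26 per subject, or 156 per cohort.
- Brought forward: 12 × 6 = 72 per cohort, or 216 over three escalations.

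**2. What the troughs already tell the SRC.** The OT half-life t (in hours) is not in the documents, so a range is assumed, with a linear one-compartment model and daily dosing. The share of steady state after n doses is 1 − 2^(−24n/t). The Day 5 trough follows dose 4 and the Day 7 profile follows dose 7.

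| t (h) | Day 5 trough, share of steady state | Day 7 AUC0-tau, share of steady state | AUC, dose 7 / dose 4 | AUC, dose 7 / dose 1 |
|---|---|---|---|---|
| 12 | 99.6% | 100% | 1.00 | 1.33 |
| 24 | 94% | 99% | 1.06 | 1.98 |
| 36 | 84% | 96% | 1.14 | 2.60 |
| 48 | 75% | 91% | 1.22 | 3.11 |
| 72 | 60% | 80% | 1.33 | 3.89 |

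The trough reaches 95% of steady state when t is at most 96/log2(20) = 22.2 h. Day 7 AUC reaches 95% when t is at most 168/log2(20) = 38.9 h.

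**3. Where the animal data point.** Protocol 8.3 reports less than two-fold AUC accumulation in dogs, similar or slightly under-proportional AUC in rats after repeated dosing, and no Cmax accumulation in either. A dose 7 / dose 1 ratio under 2 corresponds to t of about 24 h or less. In that range dose 7 AUC is within about 6% of dose 4 AUC.

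**4. Margin by dose.** Proportional scaling gives 7.6/2 = 3.8, 7.6/3 = 2.5 and 7.6/5 = 1.5 at 2, 3 and 5 mg. Protocol 6.1 calls OT exposure slightly over-proportional over 0.5 to 5 mg. With assumed power-model slopes of 1.1 and 1.2, the figure at 5 mg would be 7.6/5^1.1 = 1.29 and 7.6/5^1.2 = 1.10.

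**5. Added wait.** Let T be the assay turnaround in days (not given) and G the earliest day on which the SRC can decide. The added wait is max(G, 8 + T) − max(G, 5 + T).

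- G = 14 (14-day collection a firm gate): 0 for T up to 6; then 1, 2 and 3 days at T = 7, 8 and 9; 3 thereafter.
- G = 8 (decision possible after 8 days of safety data): T days for T up to 3, then 3.

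Over three escalations this is at most 9 days, before any extra time to run the larger batch.

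**The case against.** The strongest reply is that the sponsor chose the cut-off with the SAD results in hand. OT half-life is a SAD endpoint sampled to 168 h, and the SAD data were analysed before the MAD part. If man resembles the animals, step 3 applies and Day 7 adds little; nothing in the documents supports a half-life of 48 to 72 h. This stands, and it limits the benefit. It does rest on species similarity and linear PK, and OT was slightly over-proportional in man.

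A reader might infer that the plan breaches its own rules. It does not. Section 8.6.1 asks that emerging Cmax and AUC be benchmarked and does not demand repeated-dose values; Day 1 plus the Day 2 pre-dose sample gives both after a single dose. Section 8.5(a) is a plateau rule, separate from the toxicity rule in (b).

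A reader might also infer a hazard at 5 mg, since halving 1.5 for two-fold accumulation gives 0.76. The documents do not support that. The basis of 7.6 is not stated; if it is AUC0-inf, linear accumulation is already counted. Every MAD dose has measured SAD exposure, the SRC sees 8 days of safety data, and ten patients had at least 3 mg daily for 7 days in compassionate use without a safety issue.

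Finally, the end of the study in 12.4.4 is ambiguous. Sections 8.1 and 15.8 define it as the last subject's last visit, but Table 2 and 12.2.12 give that name to each subject's Day 14 visit. On the second reading, earlier cohorts' Day 7 results could reach later SRC meetings, which review cumulative data. The plan would still not require them for the cohort just completed. Section 8.6.2 permits earlier assay; it is simply not planned.

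**Conclusion.** The point holds as a cheap improvement. The SRC's planned PK package has 14 of 28 samples per subject and no measured Cmax or AUC after repeated dosing, while 12 more samples per subject are already in the freezer.

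The size of the gain depends on a half-life that the sponsor knows and the documents do not give. At about 24 h or less with linear PK, the troughs predict last-dose AUC to within about 6%, and Day 7 mainly confirms. Between about 22 and 39 h, Day 7 is at 95% or more of steady state and the Day 5 trough is not. Above 39 h, Day 7 is measured exposure but not yet steady state. Non-linear PK would add to the gain. The check is worth most before 5 mg, where proportional scaling leaves a margin of about 1.5. That figure is a stand-in for the sponsor's measured single-dose exposure at that dose. Confidence is moderate.

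**What to change.** Amend Protocol 8.1.2, 8.6.1 and 12.4.4 and SAP 4.1.2 so that each cohort's Day 6, Day 7 and Day 8 PK samples are assayed before the SRC decides, with priority before the step to 5 mg. Report Day 7 AUC0-tau, Cmax,ss, the accumulation ratios, and the exposure margin at the current and next dose. Day 11 and Day 14 samples can wait. State in 12.4.4 that the deferral to the end of the study does not cover the Day 6 to 8 samples. What margin is acceptable is for the sponsor and the investigator.

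There is no added blood, visit or total assay count. The cost is a pre-decision batch of 156 instead of 84 samples, the wait shown in step 5 plus run time, and possibly a substantial amendment under 15.6.1 with ethics committee and authority clearance.

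If turnaround rules this out, the sentinel's Day 6 to 8 samples can join the existing Day 5 batch (84 + 12 = 96). With the 72 h minimum stagger, the sentinel is on Day 8 or later when subjects 2 to 6 reach Day 5, so there is no added wait for sampling. One profile per cohort is a weak fallback.
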